## **Interventions**

Interventions are limited to a pin prick sensation testing at the base of the 1st toe and of the 5th toe.

## **Outcomes:**

Outcomes will include patient pain scores (rest and with activity) and the presence or absence of pin prick sensation 6 hours post LPB placement.

## **Human Subject Protection**

### **Informed Consent**

No informed consent will be obtained as patients will not be prospectively enrolled in this study, and no patient information will be obtained or otherwise collected.

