## **Methods**

Study staff will visit 10 patients, at their hospital rooms, 6 hours after a LPB and spinal block are performed for their DAA hip surgeries. Patients will be asked to verbally rate their pain, on a scale from 0 to 10, when resting and when they sit up in bed. Study staff will use a blunt needle to touch the base of the 1st toe (L5) and the base of the 5th toe (S1), without breaking the skin. Patients will be asked if they can feel “pinprick,” touch, pressure, or nothing.

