### **Exclusion**

Patients will be excluded if they do not receive a lumbar plexus block and spinal anesthesia and/or if they have peripheral neuropathy affecting their feet.

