### **Confidentiality and Privacy**

The only information taken for this study will be pain scores and presence or absence of sensation. No patient identification numbers or characteristics will be collected. Patients will be referred to by a simple number (numbers 1 through 10).

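### Do the stated reasons for not obtaining consent, which clash with the visits and data described elsewhere, call for a change to the plan?

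*Protocol*

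**What the plan says.** Under Human Subject Protection, the Informed Consent section gives two reasons for not seeking consent: "No informed consent will be obtained as patients will not be prospectively enrolled in this study, and no patient information will be obtained". The first concerns enrolment. The second concerns data, and in full it reads "no patient information will be obtained or otherwise collected".

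Other sections describe what is done:

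- **Methods:** "Study staff will visit 10 patients, at their hospital rooms, 6 hours after a LPB and spinal block are performed". At the visit, "Patients will be asked to verbally rate their pain, on a scale from 0 to 10", at rest and on sitting up. Staff then touch two toe sites with a blunt needle, and the skin is not broken.
- **Interventions:** "Interventions are limited to a pin prick sensation testing at the base of the" first and fifth toes.
- **Inclusion and Exclusion:** patients are adults having elective hip arthroplasty by the direct anterior approach. They are left out if they did not receive both the block and the spinal, or "if they have peripheral neuropathy affecting their feet".
- **Confidentiality and Privacy:** "The only information taken for this study will be pain scores and presence or absence of sensation". The same section rules out identification numbers and patient characteristics, and labels patients 1 to 10.

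**The concern.** A reader who takes the consent paragraph at its word will find it contradicted within a page. People picked by criteria, approached at a set hour and given a test that the protocol itself calls an intervention have, in ordinary usage, been prospectively enrolled. A study whose outcomes are pain scores and sensation plainly obtains information from patients, and checking for neuropathy means learning something medical about each one.

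This paragraph is also the only basis the protocol gives for going without consent. If that basis were judged unsound, one could fear that the 10 observations might be challenged. With them would go the pilot's two products: the judgement on whether 6 hours is a workable endpoint, and the pain scores meant for the power analysis of the later randomized study.

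**Working it through.** No arithmetic applies. The protocol gives no derivation for the 10 patients, and the point does not depend on a variance, an error rate or an effect size. The check is to set each reason beside the sections that bear on it, and then ask what would differ in the data if the paragraph were reworded.

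**Reason 1, no prospective enrolment.** Inclusion and Exclusion select patients for the study. Methods sends study staff to them 6 hours after the block and spinal. Interventions names a study test. Data and Safety Monitoring speaks of participants. These sections agree with one another and disagree with the reason given. No reading of the sentence reconciles them.

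**Reason 2, no patient information.** Taken literally, it conflicts with Outcomes and with Confidentiality and Privacy, which both list pain scores and sensation. It cannot have been meant literally, because the Objectives section exists to describe collecting exactly those data. Confidentiality and Privacy follows directly under the same parent heading and says that no identification numbers or characteristics are taken. Read together, the two paragraphs most plausibly mean that nothing identifying is collected. Eligibility checks do require someone to know age, procedure, block and neuropathy status, but no section says that any of this is retained.

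**What a reworded paragraph would alter:**

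| Element | Where fixed | Altered by rewording? |
|---|---|---|
| Number of patients (10) | Methods | No |
| Time of assessment (6 hours) | Methods, Outcomes | No |
| Pain at rest and on sitting up | Methods, Outcomes | No |
| Sensation at two toe sites | Methods, Interventions | No |
| Eligibility | Inclusion, Exclusion | No |
| Use of scores in a power analysis | Objectives | No |

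**Steps that the text does not supply.** The fear of lost data needs three:

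1. *A decision that could be overturned.* The protocol says only that consent will not be obtained. It reports no waiver or determination by the ethics board.
2. *A test outside usual care.* The Background names the block and spinal as the institution's standard practice. It does not say whether a sensory check after a spinal is routine. That the test is done only for research is a fair inference, but it is not stated.
3. *A rule that makes the data unusable.* None appears in the document.

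**The case for a change.** The strongest case for acting is that reason 1 is simply wrong on the protocol's own text. The generous reading of reason 2 does nothing to rescue it, and a one-paragraph correction costs almost nothing. A document that rests the absence of consent on a misdescription could mislead anyone who relies on that paragraph alone. Low risk and the absence of identifiers might well justify going without consent, but the paragraph does not invoke them.

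Most of this stands as a remark on drafting. The contradiction is genuine, and the paragraph would read better if it described patients as approached prospectively with limited anonymous data recorded. What does not stand is the step from there to a change in how the study is run. A verbal script, a pre-operative approach, a log of refusals and replacement of those who decline would all go beyond the fault shown. The same argument concedes that omitting consent could be proper on minimal-risk grounds, so the conduct of the study might need no change at all.

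Nor does the text show that patients are handled without their cooperation. Ruling out informed consent does not rule out asking, and both the pain rating and the report of what is felt require the patient to respond.

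**Conclusion.** No change to the plan follows. The consent paragraph is badly worded: one of its two reasons is contradicted by Methods, Inclusion, Exclusion and Interventions, and the other is true only if it refers to identifying information. The paragraph covers all 10 patients, but the effect shown on the sample, the measurements, their precision, any bias or the pilot's conclusions is nil. No safety consequence is shown either, since the test is a blunt touch that leaves the skin intact.

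This rests on two assumptions. The first is that the second reason is meant in the sense that Confidentiality and Privacy gives it. The second is that the ethics board judges the absence of consent on what the study actually does, which it can read in Methods and Interventions. Whether consent may properly be omitted is that board's decision, and the protocol alone cannot answer it.

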### **Confidentiality and Privacy**

The only information taken for this study will be pain scores and presence or absence of sensation. No patient identification numbers or characteristics will be collected. Patients will be referred to by a simple number (numbers 1 through 10).

### **Data and Safety Monitoring**

The principal investigator will be responsible for the overall monitoring of the data and safety of study participants. The principal investigator will be assisted by other members of the study staff.

### **Reporting of Unanticipated Problems, Adverse Events or Deviations**

Any unanticipated problems, serious and unexpected adverse events, deviations or protocol changes will be promptly reported by the principal investigator or designated member of the research team to the IRB and sponsor or appropriate government agency if appropriate.

